An internationally recognized definition for isthmocele was only agreed upon in 2019 by the European task force, which defined a cesarean scar defect as an “indentation at the site in the cesarean section scar with a depth of at least 2 mm.” This definition was further subclassified as follows: simple niche, simple niche with one branch, and complex niche (with more than one branch). A branch was defined as the thinner part of the main niche that is directed toward the serosa and has a width smaller than the main niche. Residual myometrial thickness "RMT" is the distance between the tip of the hypo echoic triangle and the surface of anterior uterine wall measured by mm.) At the apex of the main niche, the RMT is often decreased. (**Jordans IPM et al,2019**).

The present study aimed to evaluate how the use of Monocryl (monofilament synthetic

absorbable sutures) instead of Vicryl (multifilament synthetic absorbable sutures) in the continuous double-layer unlocked closure technique for low transverse uterine incisions impacts uterine scar healing after Cesarean section.

2.AIM / OBJECTIVES

To evaluate the impact of using synthetic absorbable monofilament sutures in uterine closure during caesarean delivery compared to using synthetic absorbable multifilament sutures on the development of Isthmocele.

Research Question:

Will uterine closure using synthetic absorbable monofilament sutures during caesarean delivery reduce the incidence of isthmocele compared to uterine closure using synthetic absorbable multifilament sutures?

3.METHODOLOGY:

Patients and Methods/ Subjects and Methods/ Material and Methods

- **Study Type:** A Randomized Controlled Trial.
- **Study Setting:** The study will be conducted at Ain Shams University Maternity Hospital (labour ward and the Ultrasound (Special Care unit for the fetus).
- **Study Period:** 1 year. (from December 2023 to December 2024)
- **Sampling Method:** Convenience sample from El-Demrdash hospital population that attending the ER.
- **Study Population:** The study will be conducted on (140) women divided into two equal groups.
- **Sample Justification:** Based on the results of **Saccone et al. (2022)**, with the mean defect width in mm in monofilament group 2.9 ± 0.6 and in multifilament group 3.4 ± 1 mm, alpha error 5% and power of study 80%, the required sample is 140 patients 70 in each group. The program for sample size calculation is STATA 10.

Inclusion criteria:

- Age: 20-45 years old

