- Skin closure: Reapproximation of the skin will be performed with subcuticular suture using 2-0 polypropylene nonabsorbable suture (EGYPROLENE® manufactured by Taisier-Med Obour city, Cairo, Egypt.).

Post-operative care:

- All patients will receive Non-Steroidal Anti-Inflammatory drugs immediately postoperative then one ampoule 12 hours postoperative, (**Altman, 2015**). and according to Ain Shams Maternity hospital protocol.
- Vital signs (pulse, blood pressure, temperature) of the patients will be measured four times daily during hospitalization.
- At 6 h postoperatively, urinary Foley catheters will be removed and oral intake with clear fluids will be started. (**ACOG, 2008**).
- A venous blood sample for complete blood count examination will be withdrawn after 24 hours postoperative.
- Regular antipyretic will not be used so as not to mask possible postpartum pyrexia.

- Patients will be instructed for postoperative wound care e.g.: to always keep wound dressing dry and clean and in case it gets wet it is to be dressed in an aseptic non-touch technique.
- Follow up for assessment after 1 week of delivery to check the wound, and after 6 months to undergo the Ultrasound.

Outcomes:

Primary outcome: the incidence of isthmocele by transvaginal ultrasound 6 months after delivery.

Isthmocele is defined as an anechoic defect communicating with the endometrial cavity at the anterior wall of the lower uterine segment.

For each case the following isthmocele measurements will be obtained:

1. The thinning extent, calculated by a ratio between (a) and (b).
 - (a): thickness of the residual myometrium over the defect.
 - (b): total intact myometrium. A severe deficiency occurs when more than 50% of myometrium is lost at the niche scar site.
2. Width of isthmocele (c)
3. Depth of isthmocele (d)

Furthermore, we will record the shape of the defect (i.e., triangular, round, or oval). Moreover, the residual myometrial thickness will be measured. In case of isthmocele, RMT overlying the defect and the adjacent myometrial thickness fundal to the defect will be recorded. According to previous literature, the diagnosis of isthmocele was made in case of depth of the defect at least 2.00 mm in the longitudinal plan. (**Naji O et al, 2012**).

[figure not shown]

Figure 1.

Secondary outcomes:

1. Amount of blood loss.

ABL = weight kg * age sex factor (65ml/ kg)*initial HGB(g/dl)-final HGB(g/dl) / 12-hours postoperative"./ intial HGB (g/dl) (M. E. Brecher,2003)

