2. Need for extra hemostatic sutures.
3. Need for blood transfusion.

4. Wound infection.
5. Hospital stay after the delivery.
6. Post-operative fever.

(Defined as a temperature higher than 38 c on two consecutive postoperative days or higher than 39 c on any postoperative day). **(Abdelmaseeh TA et al, 2022)**

7. Primary Postpartum hemorrhage. (Defined as Cumulative blood loss greater than 1000 mL with signs and symptoms of hypovolemia within 24 hours of the delivery). **(ASOG,2017)**.

- **Statistical analysis:**

Based on the results of Saccone et al 2022 , with the mean defect width in mm in monofilament group 2.9 ± 0.6 and in multifilament group 3.4 ± 1 mm, alpha error 5% and power of study 80%, the required sample is 140 patients 70 in each group . The program for sample size calculation is STATA 10.

- **Ethical Consideration:**

This study will be done after approval of the ethical committee of the department of obstetrics and gynecology, faculty of medicine, Ain Shams University. Informed consent will be taken from all participants before recruitment in the study, and after explaining the purpose and procedures of the study. The investigator will obtain the written, signed informed consent of each subject prior to performing any study specific procedures on the subject. The investigator will retain the original signed informed consent form. All laboratory specimens, evaluation forms, reports, and other records that leave the site will not include unique personal data to maintain subject confidentiality. The study will be based on the investigator self-funding.

Protocol approval:

Before the beginning of the study and in accordance with the local regulation followed, the protocol and all the corresponding documents will be declared for ethical and research approval by the council of OB/GYN Department, Ain Shams University according to the the ethical committee

Patient right to withdraw

4. REFERENCES:

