Chorioamnionitis in that pregnancy	
Medical history	
Surgical history	
Pre-operative haemoglobin level	
Post-operative haemoglobin level	
Total blood loss	
Number of received blood components	
Procedure time	

ICU admission	
Hospital stay	
Post-operative fever	
Wound infection	
Trans vaginal US after 6 months → Isthmocele? Yes or NO if Yes → Isthmocele measurements will be obtained.	
Bladder injury in that Cesarean section	
Post-partum hemorrhage

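### The blood-loss formula has no term for transfused blood, so it understates loss in any woman given red cells before the final haemoglobin sample

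*Protocol*

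**What the plan says.** All references are to the Protocol, section 3 (Methodology), and the Case Record Form (Form 3).

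- **Blood loss.** Secondary outcome 1 is defined by one formula: "ABL = weight kg * age sex factor (65ml/ kg)*initial HGB(g/dl)-final HGB(g/dl"), divided by the initial Hb. Brackets are missing, but the evident intention is weight × 65 mL/kg × (initial Hb − final Hb) / initial Hb.
- **Time of the final Hb.** The formula carries the words "final HGB(g/dl) / 12-hours postoperative". The Post-operative care list schedules one count: "A venous blood sample for complete blood count examination will be withdrawn after 24 hours postoperative".
- **Transfusion.** Secondary outcome 3 is "Need for blood transfusion", and the form has a row for "Number of received blood components". Neither is linked to the formula, and the protocol does not say how transfused women are handled in the blood-loss outcome.
- **Haemorrhage.** Secondary outcome 7 is defined as "Cumulative blood loss greater than 1000 mL with signs and symptoms of hypovolemia within 24 hours of the delivery". No method for measuring that loss is given.
- **Form.** There is one row for "Total blood loss", one for the post-operative Hb, and a separate row for haemorrhage. There is no field for the time of the Hb sample or of a transfusion.

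**The concern.** A formula based on the fall in Hb works only if bleeding is what changed the Hb. Transfused red cells push the final value back up, and the formula reads this as less bleeding. The error runs in one direction and grows with each unit, so it is largest in women who needed most blood. If one suture led to more bleeding and more transfusion, its calculated loss would be pulled down more than that of the other arm. Settling the brackets or the 12-hour versus 24-hour conflict would not remove the problem, because either sample can follow a transfusion.

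**Working it through.** The protocol gives no worked blood-loss figure to reproduce, so the check evaluates its formula directly.

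**Inputs.** From the protocol: 65 mL/kg, the formula read as intended, and the 1000 mL threshold. Assumed, because the protocol gives no values: weight 70 kg, initial Hb 11 g/dL, and a rise of r = 1 g/dL per red-cell unit, with r varied.

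**Understatement per unit.** If u units are given before the final sample, the final Hb is higher by r × u. The formula then falls short by weight × 65 × r × u / initial Hb.

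**Example.** Blood volume = 70 × 65 = 4550 mL. Suppose that bleeding alone would take Hb from 11 to 8 g/dL.

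| Units before sample | Final Hb (g/dL) | Formula | Result |
|---|---|---|---|
| 0 | 8 | 4550 × 3/11 | 1241 mL |
| 1 | 9 | 4550 × 2/11 | 827 mL |
| 2 | 10 | 4550 × 1/11 | 414 mL |

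**Range of the per-unit error.**
- Same woman: r = 0.5 gives 4550 × 0.5/11 = 207 mL; r = 0.7 gives 290 mL; r = 1.3 gives 538 mL.
- At r = 1 over 60–90 kg and initial Hb 10–13 g/dL: from 60 × 65/13 = 300 mL to 90 × 65/10 = 585 mL.
- Over the same weights and Hb values with r = 0.5–1.5: 150 to 878 mL.

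**Negative values.** At 75 kg and initial Hb 11.5 g/dL, one unit hides 4875/11.5 = 424 mL. A true loss of 800 mL with two units is returned as 800 − 848 = −48 mL.

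**The 1000 mL line, if the formula supplies it.** In the 70 kg example, one unit takes any true loss between 1000 and about 1414 mL below 1000 mL; two units do so up to about 1827 mL.

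**Effect on an arm mean (70 women, assumed transfusion rates, 414 mL per unit).**
- 2% transfused, one unit each: 0.02 × 414 = about 8 mL.
- 5% transfused, one unit each: 0.05 × 414 = about 21 mL. A 5% versus 2% imbalance therefore shifts the difference between arms by about 12 mL.
- 2 of 70 women with two units each: 2 × 827/70 = about 24 mL; 5 of 70: about 59 mL.

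**The case against.** Four objections deserve weight.

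**Few women may be affected.** Entry is limited to elective primary caesarean, and abnormal placentation, previous uterine surgery, fibroids, drugs affecting bleeding and medical comorbidity are excluded. No transfusion rate is given. This stands: the assumed rates above shift an arm mean by only about 8 to 59 mL. A reader might infer that the comparison of mean blood loss is seriously distorted; the documents do not support that.

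**The link to haemorrhage is not stated.** A reader might infer that haemorrhage cases will be missed because the formula decides the 1000 mL criterion. The protocol never says so. Its definition also needs signs and symptoms of hypovolemia, and the form records haemorrhage in its own row. This stands too, so the consequence is conditional. It cannot be dismissed, because no other way of measuring loss is described and both parts of the definition must be met: signs of hypovolemia would not rescue a woman whose loss reads below 1000 mL.

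**Crossing the line depends on the assumptions.** In the example, one unit must hide more than 241 mL, so r must exceed 241/414 = about 0.58 g/dL. At r = 0.5 the formula gives 1241 − 207 = 1034 mL, still above 1000 mL. The understatement remains; only the crossing is lost.

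**A statistical analysis plan could deal with it, and transfusion is reported separately.** A plan not shown might adjust or set apart transfused women. But the protocol fixes the formula itself, and the form records neither the times nor the type of component. An analyst working from that form could not tell which Hb values followed a transfusion.

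**Conclusion.** The point holds as a defect in the definition of a secondary outcome. Applied as written, the formula gives too small a loss for every woman who receives red cells before the final Hb sample: about 414 mL per unit at 70 kg, initial Hb 11 g/dL and a 1 g/dL rise, or 207 to 538 mL for rises of 0.5 to 1.3 g/dL. These inputs are assumptions; the direction of the error does not depend on them. The effect on arm means is likely small. The exposure lies in the upper tail of blood loss, and in the haemorrhage count only if the formula supplies the 1000 mL figure. The primary outcome, isthmocele at 6 months, is not touched. It should be corrected because the error is systematic and cheap to prevent, not because it threatens the trial's main conclusion.

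**What to change.** 1. Add a transfusion term: loss = weight × 65 × (initial Hb − final Hb + r × u) / initial Hb, where u is the number of red-cell units given before the final sample. State r in advance with a sensitivity range, for example 0.5 to 1.5 g/dL. In the example with one unit and a final Hb of 9, this gives 4550 × 3/11 = 1241 mL at r = 1, and 1034 to 1448 mL over that range.
2. On the form, record red-cell units separately from other components, with the times of transfusion and of the Hb sample. The present count does not separate them, and adding back Hb for every component could overcorrect.
3. State which measurement decides the 1000 mL criterion, and do not decide it on an uncorrected Hb taken after transfusion.
4. Reconcile the 12-hour and 24-hour statements, since the sample time determines which transfusions count towards u.

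Substituting the last Hb before transfusion is not an adequate alternative: no such sample is scheduled, and it would miss later bleeding.

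The cost is a revised definition and a few form fields, with no extra patients or tests. The downside is that the corrected loss rests on an assumed rise per unit, which is why the sensitivity range is needed.

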Chorioamnionitis in that pregnancy	
Medical history	
Surgical history	
Pre-operative haemoglobin level	
Post-operative haemoglobin level	
Total blood loss	
Number of received blood components	
Procedure time	

ICU admission	
Hospital stay	
Post-operative fever	
Wound infection	
Trans vaginal US after 6 months → Isthmocele? Yes or NO if Yes → Isthmocele measurements will be obtained.	
Bladder injury in that Cesarean section	
Post-partum hemorrhage
